Analysis Sets	The primary analysis set will consist of all subjects who were enrolled. The subject will be considered to be enrolled after arterial access is established and the Valiant Evo Thoracic Stent Graft System is introduced.
	A secondary analysis set will be the Per-Protocol population. This analysis set is comprised of all enrolled subjects who met inclusion and exclusion criteria, received the test device and completed 30-day follow-up (including death but excluding withdrawal or lost to follow-up subjects within the 30-day follow-up period).
Data Oversight	A Data Monitoring Committee, Clinical Events Committee, and imaging core lab will be established to independently evaluate subject health status, device performance, and identify any safety concerns regarding subjects' well-being. Contact details of the committees and the core lab will be available in the investigational site file.

Safety Monitoring	Medtronic Clinical Operations [name]	
Monitoring	Medtronic Clinical Operations [name]	

B GENERAL INFORMATION

B.1 Introduction

Background:

An aortic aneurysm is defined as a dilatation of the aortic vessel greater than 50% of its normal diameter for a given segment of the adhering normal vessel. An aneurysm of the Descending Thoracic Aorta (DTA) is defined as involving any portion of the thoracic aorta distal to the LSA and extending to above the diaphragm. In adults, the diameter of the aorta is about 30 mm at the aortic root and about 25 mm at the level of the diaphragm. Age is the major influential factor in the aneurysm diameter size increase and all diameters increase with age. It has been reported that aortic diameters increase about 1 mm per decade during adulthood. Generally, a diameter in the thoracic aorta > 4.5 cm is considered aneurysmal. 1, 2,3,4,5

A thoracic aortic aneurysm (TAA) is a life-threatening condition. Annually, the incidence of TAA in a population-based study is 10.4 per 100,000 person-years, and the DTA is involved in about 40% of those cases.⁶ The number of people diagnosed with an aneurysm of the DTA is thought to be increasing. Factors that contribute to this rise include increased longevity of the population and improved diagnostic capability.^{6,7,8}

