- · Aneurysm-Related Mortality within 365 days
- · MDEs within 365 days
- All AEs within 365 days including:

- MAEs
- SAEs
- Secondary procedures within 365 days
- Loss of stent graft patency within 12 months based on imaging findings
- Endoleaks at 12 months based on imaging findings
- Stent graft migration at 12 months as compared to 1-month imaging
- Aneurysm expansion > 5mm at 12 months based on imaging findings relative to the 1month visit

C.2.2.4 24, 36, 48 and 60-month Secondary Endpoints

The following secondary endpoints will be evaluated:

- · All-cause mortality up to each timepoint
- Aneurysm-Related Mortality up to each timepoint
- · MDEs up to each timepoint
- · All AEs up to each timepoint:
 - MAEs
 - SAEs
- Secondary procedures up to each timepoint
- Loss of stent graft patency (site-reported) up to each timepoint based on imaging findings
- Endoleaks (site-reported) at each timepoint based on imaging findings
- Stent graft migration (site-reported) at each timepoint as compared to 1-month imaging
- Aneurysm expansion > 5mm (site-reported) at each timepoint based on imaging findings relative to the 1-month visit

C.2.3 Additional observations

The following acute procedural observations and clinical utility measures will be analyzed:

- · Mean duration (min) of procedure
- Proportion of subjects who underwent general anesthesia
- · Proportion of subjects who underwent percutaneous access
- Proportion of subjects requiring blood transfusions
- · Mean number of units of blood transfused, if required
- Mean volume (cc) of estimated blood loss
- . Mean length of time (hours) in intensive care unit
- Mean length of time (days) of hospital stay (from the index procedure to hospital discharge)

Health-related quality of life outcomes will be assessed at all scheduled follow-up visits using the EQ-5D questionnaire.

C.3 Study Hypothesis

The Valiant Evo US Clinical Trial will focus on balancing pre- and post-market clinical data to establish safety and effectiveness.

The primary study endpoint will be tested against a performance goal of 16% at 30 days:

 H_0 : $p \ge 16\%$ vs. H_a : p < 16%,

where p denotes the true event rate of primary study endpoint in the target population.

If the null hypothesis (H₀) is rejected at the one-sided 0.025 statistical significance level, it is considered that the performance goal for the primary endpoint has been reached.

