A Data Monitoring Committee, Clinical Events Committee, and imaging core lab will be established to independently evaluate subject health status, device performance, and identify any safety concerns regarding subjects' well-being. An imaging core lab will not be used to perform independent imaging assessments regarding device performance beyond 12 months of follow-up.

C.6 Randomization and blinding

The study is a single arm study, therefore neither randomization nor blinding are applicable to this clinical trial.

C.7 Sample size

Globally, a total of 100 subjects will be concurrently enrolled in the United States and outside the United States to support the primary endpoints. Up to 50% of subject data used to support PMA approval may come from subjects enrolled at sites outside of the US under a separate CE Mark study protocol; called the Valiant Evo International Clinical Trial protocol.

The Valiant Evo International Clinical Trial protocol and Valiant Evo US Clinical Trial protocol will be identical with respect to the inclusion/exclusion criteria.

One hundred (100) enrolled subjects will ensure 87 evaluable subjects at 30 days. The primary endpoint analysis will be completed upon 87 evaluable subjects reaching the 30 day endpoint. The data from these 87 evaluable subjects at 30-days will be used to file the PMA submission. Based on Valor II study results, Valiant Evo is expected to perform similarly and have 6% of MDEs combined with access and/or deployment failures at 30 days. The sample size of 87 evaluable subjects will provide 85% statistical power for the study hypothesis. The type I error is controlled at the one-sided 0.025 level.

True rate of MDEs combined with access 6% and/or deployment failures at 30 day with Valiant Evo Performance Goal 16% Significance level 0.025 One-sided binomial test Statistical test Evaluable sample size Minimum of 100 subjects Enrollment enrolled to ensure 87 evaluable subjects Statistical power from the 87 evaluable 85% subjects

Table C-1: Power Analysis

C.8 Number of Investigational sites and study duration

The Valiant Evo Global Clinical program will be conducted at up to 37 sites worldwide, with at least 50% of the clinical sites coming from the United States. Inclusion will be halted at sites

that reach the 20% inclusion cap. There will be no minimum number of subjects for a single investigational site.

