ADE Adverse Device Effect

AE Adverse event

ASA American Society of Anesthesiologists
ASADE Anticipated serious adverse device effect

AV Arteriovenous

CEC Clinical Event Committee
CIP Clinical Investigation Plan

CRF Case Report Form

CT Computed Tomography
CVA Cerebral Vascular Incident

CRO Clinical Research Organization

DD Device Deficiency

DMC Data Monitoring Committee
DTA Descending Thoracic Aorta

DTAA Descending Thoracic Aortic Aneurysm

EC Ethical Committee

eCRF Electronic Case Report Form

EDC Electronic Data Capture

FDA Food and Drug Administration

IB Investigator Brochure
ICU Intensive Care Unit

ICH-GCP International Conference on Harmonization - Good Clinical Practice

IDE Investigational Device Exemption

IFU Instructions for Use

INR International Normalized Ratio IPR Independent physician reviewer

IRB Institutional Review Board

ISO International Organization for Standardization

MAE Major Adverse Event
MDE Major Device Effect
MI Myocardial Infarction

MRA Magnetic Resonance Angiography

MRI Magnetic Resonance Imaging
PET Polyethylene terephthalate

PMA Premarket Approval RA Regulatory Affairs

RAE Regulatory Affairs Europe
ROPI Report of Prior Investigations
SADE Serious Adverse Device Effect

SAE Serious Adverse Event

SOP Standard operating procedure
TAA Thoracic Aortic Aneurysm

TEE Transesophageal echocardiography
TEVAR Thoracic Endovascular Aortic Repair
UADE Unanticipated Adverse Device Effect

USADE Unanticipated Serious Adverse Device Effect

L.2 Definitions

L.2.1 Primary and Secondary Endpoints

Term	Definition
Access failure	Inability to insert device due to mechanical failure or anatomic exclusions of the femoral or iliac arteries
Deployment Failure	Deployment failure due to subject anatomy or mechanical failure. This specifically refers to deployment of the stent graft from the delivery system.
Adverse Event (AE)	See section F.6.1
Serious Adverse Event (SAE)	See section F.6.1
Major Adverse Events (MAEs)	Major Adverse events include the occurrence of any of the following :
	 Respiratory complications: atelectasis/pneumonia, pulmonary embolism, pulmonary edema, respiratory failure.
	Renal complications: renal failure, renal insufficiency.
	 Cardiac complications: myocardial infarction (MI), unstable angina, new arrhythmia, exacerbation of congestive heart failure (CHF).
	 Neurological complications: new cerebrovascular accident (CVA), cerebrovascular embolic events, paraplegia, paraparesis.

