7.1.3. Analysis Sets

Analysis set to be used for each endpoint analysis will consist of all subjects who were enrolled. The subject will only be considered enrolled when arterial access is established and an attempt to introduce the Valiant Evo Thoracic Stent Graft is made.

Valiant Evo US Clinical Trial Statistical Analysis Plan Version 2.0 Nov 1, 2017

This document is electronically controlled. Printed copies are considered uncontrolled.

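### The synopsis analysis sets do not match the rest of the plan: the enrolment point is worded differently, and a synopsis-only Per-Protocol set drops subjects who are already failures on the primary endpoint

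*Protocol*

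**What the plan says.** **Enrolment, which fixes the primary set.** The protocol synopsis (Analysis Sets) counts a subject as enrolled after arterial access is established and "the Valiant Evo Thoracic Stent Graft System is introduced". Protocol F.1 and SAP sections 5 and 7.1.3 require arterial access and that "an attempt to introduce the Valiant Evo Thoracic Stent Graft is made". Protocol H.1 defines the primary set as all enrolled subjects and sends the reader to F.1 for the meaning of enrolled.

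**Per-Protocol set.** The synopsis adds a secondary set of enrolled subjects who met the eligibility criteria and who "received the test device and completed 30-day follow-up". Deaths are kept; withdrawals and losses to follow-up within the 30 days are excluded. The set appears neither in H.1 nor in the SAP. SAP 7.1.3 uses all enrolled subjects for each endpoint analysis.

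**Endpoint.** The primary composite (protocol C.2.1) counts access and/or deployment failures and MDEs within 30 days. Protocol L.2.1 defines access failure as "Inability to insert device due to mechanical failure or anatomic exclusions of the femoral or iliac arteries". SAP 7.9 scores a subject as a failure if access or deployment failed or an MDE occurred within 30 days.

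**Follow-up of subjects without an implant.** Under F.1 and F.2.2, enrolled subjects without an implant, and those with primary conversion, are followed for one month.

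**The concern.** An analysis set should not depend on the outcome it is used to estimate. Receiving the device is close to the opposite of having an access failure, so a set that requires receipt cannot contain that part of the endpoint. It also loses deployment failures and primary conversions in which nothing was implanted. Missing data is no justification: these subjects are followed for a month and are already failures.

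The enrolment wording raises a related question. If a subject enters only once the system has been introduced, a failed insertion may be read as leaving the subject unenrolled, and so outside the primary set as the synopsis describes it.

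At stake are the correctness of the population stated in the synopsis and the meaning of any Per-Protocol rate that is reported. Access deserves care here because protocol B.1 presents the lower delivery profile as a way to improve vascular access.

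**Working it through.** **1. The plan's own figure.** Inputs from protocol C.3 and C.7: performance goal 16%, expected composite 6%, one-sided alpha 0.025, 87 evaluable subjects, exact binomial test. The plan states: "The sample size of 87 evaluable subjects will provide 85% statistical power for the study hypothesis".

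- P(X ≤ 7 | n = 87, p = 0.16) = 0.0233, which is within 0.025.
- P(X ≤ 8 | n = 87, p = 0.16) = 0.0495, which is not. The test therefore passes with at most 7 failures.
- Power = P(X ≤ 7 | n = 87, p = 0.06) = 0.849. The stated 85% reproduces.

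The 6% in this calculation already includes access and deployment failures: the device is expected to "have 6% of MDEs combined with access and/or deployment failures at 30 days".

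**2. Who is in which set.**

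| Subject | Score on primary endpoint (SAP 7.9) | Primary set by F.1, H.1, SAP | Primary set by synopsis wording | Per-Protocol set |
|---|---|---|---|---|
| Insertion attempted and failed (access failure) | Failure | In | Out, read literally | Out |
| Deployment failure or primary conversion, no implant | Failure | In | In (system was introduced) | Out |
| Deployment failure, device still received | Failure | In | In | In, if otherwise eligible and followed |
| MDE, then withdrawal before day 30 | Failure (counted in m, SAP Table 5) | In | In | Out, read literally |
| Death within 30 days, device received | Failure if device-related or another MDE occurred | In | In | In, if eligible |
| Event-free, successful implant, withdrawal after day 1 and before day 30 | Success (counted in k, SAP Table 5) | In | In | Out |

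The two wordings of enrolment differ only in the first row.

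**3. Direction.** Removing f known failures from x failures among n subjects changes the rate by (x − f)/(n − f) − x/n = −f(n − x)/[n(n − f)], which is never positive. These exclusions alone can only lower the rate.

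Removing event-free subjects works the other way. With assumed counts of 6 failures in 100 enrolled, all implanted and followed, and 5 event-free early withdrawals, the rate goes from 6/100 = 6.0% to 6/95 = 6.3%.

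**4. Size.** Let p = 0.06 be the planned composite rate and q the share of all subjects who are failures without an implant. The documents give no value for q; 1 to 3 percentage points is an assumption. Removing only those subjects gives (p − q)/(1 − q):

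- q = 0.01: 0.05/0.99 = 5.1%
- q = 0.02: 0.04/0.98 = 4.1%
- q = 0.03: 0.03/0.97 = 3.1%

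Among 87 subjects this range of q is 87 × 0.01 = 0.9 to 87 × 0.03 = 2.6 people, against 87 × 0.06 = 5.2 expected failures.

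**The case against.** The strongest reply is that the test that matters is already protected. H.1 points to F.1, F.1 and the SAP enrol at the attempt, and SAP 7.9 counts access and deployment failures in all enrolled subjects. That stands. A reader might infer from the synopsis that the primary rate is biased low or the type I error inflated. The documents do not support this: it would require the synopsis wording to override F.1, H.1 and the SAP, and even then only access failures would be affected.

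A reader might also infer that a Per-Protocol result is bound to look better, or that it loses one of the two endpoint components entirely. Neither follows. The set also drops eligibility violators and event-free withdrawals, which can move the rate either way, and deployment failures in subjects who still received a device remain.

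It is fair to add that requiring treatment received is the usual meaning of per-protocol, that no hypothesis test is attached to the set, and that no document says it supports the primary result. It is also unclear whether a partial insertion counts as introduced, since the device deficiency list in L.2.3 separates access failure from insertion failure.

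These points limit the concern but do not remove it. Here the device not being received is often itself the endpoint event. Nor does the SAP's silence withdraw the set, because SAP section 3 makes the protocol the primary resource where clarification is needed.

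**Conclusion.** Two wording defects stand, both minor.

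1. The synopsis states an enrolment point that conflicts with F.1 and the SAP. Read literally, it leaves a failed insertion outside the primary set. The operative definition does not, so the primary test is unaffected.
2. The synopsis-only Per-Protocol set removes subjects already known to have failed on the primary endpoint. That part of its definition can only lower the rate; the net direction, once its other exclusions are included, is not fixed.

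The illustrative size is a fall from 6.0% to between 5.1% and 3.1%. This rests on the assumed 1 to 3 points of never-implanted failures and on removing nobody else. The documents allow no firmer estimate, and no planned test depends on it.

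**What to change.** - **Synopsis, enrolment:** replace the wording with that of F.1 and SAP 7.1.3, so that enrolment occurs at the attempt to introduce the device.
- **Per-Protocol set:** either delete it from the synopsis, consistent with SAP 7.1.3, or define it in both documents as enrolled subjects without a major eligibility deviation who have known 30-day status or have already failed. Access and deployment failures and MDEs then stay in as failures, whether or not a device was implanted or day 30 was completed.

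The cost is a few lines in the synopsis and, if the set is kept, in H.1 and SAP 7.1.3. The design is unchanged: 87 evaluable subjects, at most 7 failures to pass, exact alpha 0.0233 and power 84.9%. The downside is that a Per-Protocol rate, if reported, may be slightly less favourable. The alignment leaves one boundary as it is: a subject in whom arterial access is never established is not enrolled under either wording.

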Number of subjects	Globally, a total of 100 subjects will be concurrently enrolled in the United States and outside the United States to support the primary endpoints. Up to 50% of subject data used to support PMA approval may come from subjects enrolled at sites outside of the US under a separate CE Mark study protocol; called the Valiant Evo International Clinical Trial protocol. The primary endpoint analysis will be completed upon 87 evaluable subjects reaching the 30 day endpoint.
	The data obtained from these 87 evaluable subjects will be used to support PMA-S Approval of the Valiant Evo Thoracic Stent Graft System.
	The Valiant Evo US Clinical Trial protocol and Valiant Evo International Clinical Trial protocol will be identical with respect to the inclusion/exclusion criteria.
Number of Sites	The Valiant Evo Global Clinical program will be conducted at up to 37 sites worldwide, with at least 50% of the clinical sites coming from the United States.
Clinical Procedures and Follow Up Schedule	 Subjects require follow-up evaluations at the following time points: 1 month following the index procedure (30 ± 15 days) 6 months following the index procedure (183 ± 30 days) 12 months following the index procedure (365 ±60 days) 24 months following the index procedure (730 ± 60 days) 36 months following the index procedure (1095 ± 60 days) 48 months following the index procedure (1460 ± 60 days) 60 months following the index procedure (1825 ± 60 days)
	For subjects that re-consent to extended study follow up, the assessments as performed during the 12-month visit are to be repeated at 24, 36, 48 and 60 month visits.
Principal Investigator	[name] Director, Vascular Surgery Cedars-Sinai Medical Center [name]
Indications for Use	The Valiant Evo Thoracic Stent Graft System is indicated for the endovascular repair of fusiform aneurysms and saccular aneurysms/penetrating ulcers of the descending thoracic aorta (DTA) in patients having the appropriate anatomy including the following:
	Iliac or femoral artery access vessel morphology that is compatible with vascular access techniques, devices, or accessories
	 Nonaneurysmal aortic diameter from 16 mm to 42 mm Nonaneurysmal aortic proximal neck length ≥20 mm (for FreeFlo configuration) and ≥25 mm (for Closed Web configuration)

	Distal neck length ≥20 mm

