IDE cohort will be followed up to 1-year and the primary endpoint will be tested against a 20% performance goal at 1 year for the post-approval analysis. Refer to Appendix L-6- PMA-S Post Approval analysis.

C.4 Study population

The study population will include those subjects who are appropriate candidates for endovascular repair of DTAA, and who meet the Inclusion/Exclusion criteria (defined in Section D).

C.5 Study design

The Valiant Evo US Clinical Trial is a prospective, multi-center, pre-market, non-randomized, single-arm trial. The trial is designed to assess the safety and effectiveness of the Valiant Evo Thoracic Stent Graft System in subjects with a descending thoracic aortic aneurysm (DTAA) who are candidates for endovascular repair.

The clinical performance of the Valiant Evo Thoracic Stent Graft will be evaluated in a total of 100 subjects with a hypothesis-based 30-day premarket composite safety and effectiveness endpoint.

The proposed primary composite safety and effectiveness endpoint is based on the proportion of subjects who experienced:

- (a) Access and/or deployment failures; and/or
- (b) Major Device Effect (MDE) within 30 days post index procedure

MDEs include the occurrence of any of the following:

- · Device-related secondary procedures
- Device-related mortality
- Conversion to open surgery
- Thoracic aortic aneurysm rupture

This primary composite endpoint will be compared to a PG of 16% MDE rate at 30 days.

All subjects included will continue to be followed under this investigational protocol beyond the 30-day primary endpoint out to 60 months post-implantation. Subjects will have required follow-up evaluations at the following time points:

- 1-month following the index procedure
- 6-months following the index procedure
- 12, 24, 36, 48 and 60-months following the index procedure

All subjects were consented for up to 2 years of follow-up. This was to accommodate any global clinical investigational requirements, if required. Subjects already enrolled and willing to extend

their follow-up from 12 to 60 months are to be re-consented. Enrolled subjects who decline to continue to participate in follow-up beyond 12-months shall exit the study upon the completion of their 12-month visit.

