1 Month (± 15 days)	15	30	45
6 Month (183 ±30 days)	153	183	213
12 Months (365 ±60 days)	305	365	425
24 Months (730 ±60 days)	670	730	790
36 Months (1095 ±60 days)	1035	1095	1155
48 Months (1460 ±60 days)	1400	1460	1520
60 Months (1825 ±60 days)	1765	1825	1885

Table F-1: Post-Implantation Follow-Up Visit Schedule and Windows

At all required follow-up visits subjects will undergo the following assessments and procedures:

- Physical Examination
- Chest CT/MRI with contrast
- EQ-5D questionnaire
- Adverse event assessment

A CT/MRI with contrast acquired at discharge (or before day 15) due to medical necessity may be used to meet the 1-month follow-up visit CT/MRI requirement if a CT/MRI with contrast cannot be obtained within the 1-month follow-up window due to the subject's health status based upon physician discretion.

If conversion to open repair is required during the follow-up period, then the subject will be followed for 30 days after the conversion, at which time the subject will be exited from the study.

F.3 Data collection requirements

Clinical data will be collected preoperatively to establish eligibility, at baseline, during the index procedure, throughout the hospital stay, and postoperatively at the required (and any interim imaging) follow-up visits described in Section F.2. The data collection schedule is summarized in Table F-2. Imaging source data will be sent to a Core Lab for analysis up to the 12-month follow-up visit. Any interim imaging of the stent graft region but not linked to a study visit should be recorded on the Interim Image eCRF (e.g. imaging performed as standard of care beyond the protocol required time points and/or when performed further to any issue observed at previous imaging Follow-up).

Imaging source data beyond 12-months post-index procedure will not be sent to the Core Lab for analysis. Instead, study sites are to report the results of the imaging performed as standard of care and in line with local and site requirements directly on the e-CRF. Routinely acquired images may be required for adjudication purposes in case of CEC adjudication or any other safety event.

Study data will be collected using electronic case report forms (eCRFs) as described in Section G.1. Clinical investigators must electronically review and approve all eCRFs. Medtronic monitors will perform source document verification of the eCRFs. The monitoring strategy will be defined in the monitoring plan.

Table F-2: Data Collection Schedule

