DATA	Screening / Baseline	Index Procedure	Hospital Discharge	1-Mo. F/U (±15 days)	6-Mo. F/U ^d (+ 30 days)	12-Mo. F/U (+ 60 days)	24, 36, 48 & 60-Mo. F/U (+ 60 days)
GENERAL							
Informed Consent	*						
Inclusion Criteria/ Exclusion Criteria	*						
Physical Examination	~			✓	>	~	✓
Medical History	✓						
Current Health Status and Risk Factors	√						
Device and Procedure Information		✓					
Pre-implant Adjunctive Procedures		✓					
Hospital Discharge Information			✓				
Adverse event assessment	√a	✓	✓	✓	√	✓	✓
EQ-5D questionnaire	✓			✓	✓	✓	✓
IMAGING							
CT/MRI with contrast ^b	√g			√c,e,g	√e.g	√e.g	√e,h
Angiography		√f					

^a In case of screen failures, investigators will be requested to enter safety information in the eCRF from time point of enrollment until time point of screen failure

^b CT evaluation may include "3-phase technique", volume studies, 3-D reconstruction, or computer-aided measurements

^c A CT/MRI with contrast acquired at discharge (or before Day 15) due to medical necessity may be used to meet the 1-month follow-up visit CT/MRI requirement if a CT/MRI with contrast cannot be obtained within the 1-month follow-up window due to the subject's health status based upon physician discretion.

^d For subjects enrolled in the Valiant Evo International Clinical Trial in European countries, a six month follow up visit is not required per protocol.

^e MRI with contrast may be used for those patients experiencing renal failure or who are otherwise unable to undergo contrast-enhanced CT scan, with Transesophageal echocardiography (TEE) being an additional option in the event of suboptimal MR imaging.

^f Required to complete Procedure eCRF but not expected to be submitted to Medtronic or Core Lab unless further analysis is needed.

g Imaging assessed by core lab.

^h Upon sponsor request, core lab analysis of imaging may be required.

F.4 Role of the sponsor's representatives

Sponsor's representatives may provide support as required for the clinical study, including technical support during implant. The sponsor representative is an experienced expert of device sizing, placement and the technical features of the device and will advise the implanting physician during the implant procedure if needed. The sponsor representative will not be involved actively during the placement and deployment of the Valiant Evo Thoracic Stent Graft System.

F.5 Source documents

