Secondary procedure	Any endovascular or surgical procedure performed following the completion of the operative initial implantation procedure (thus on subsequent occasion after final closure of the last artery access site) which involves the targeted vascular segment treated by the Valiant Evo Thoracic Stent Graft System in which there is either manipulation of the existing Valiant Evo Thoracic Stent Graft, implantation of any additional stent graft devices or manipulation of covered branch(es) by implanted stent grafts.
Conversion to open surgery	Primary Conversion : Conversion from endovascular to open repair required at the time of the original procedure, to treat the lesion intended to be treated with the Valiant Evo Thoracic Stent Graft System.
	Secondary Conversion : Conversion from endovascular to open repair required at a time beyond the initial endovascular procedure, to treat the lesion originally treated with the Valiant Evo Thoracic Stent Graft System.
Thoracic Aortic Aneurysm rupture	Rupture or perforation of the targeted thoracic aneurysmal sac as detected by angiography, CT scan, or direct observation at surgery or autopsy.

Term	Definition
	Aneurysm rupture should be reported as either procedure- related aneurysm rupture (i.e., perforation of the aneurysm during the course of the implantation procedure) or as a late aneurysm rupture that follows device deployment.
	Excluded are aneurysms in anatomic areas other than the targeted segment treated by the Valiant Evo Thoracic Stent Graft System.
Aneurysm expansion	Aneurysm maximum diameter increase > 5 mm as compared to the 1- month contrast enhanced imaging measurements
Stent graft migration	Evidence of proximal or distal movement of the stent graft (>10 mm) relative to fixed anatomic landmarks (e.g. supra aortic trunks, coeliac trunk), which is not due to remodeling of the subject's vasculature.
	The 1-month imaging will be used as the baseline for this determination.
Loss of stent graft patency	Defined as a 100% complete blockage (occlusion) of the lumen diameter of any implanted stent graft component(s) as evidenced by CT, angiography, ultrasound, or other appropriate imaging modality, and/or operative pathological analysis.
Endoleak	Defined by the presence of contrast-enhanced blood outside the lumen of the endoluminal graft but within the aneurysm sac. Endoleaks are classified as follows:
	Type I a – Leak at the proximal graft attachment site

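### SAP 7.9 takes the numerator of the 24- to 60-month by-visit imaging rates from the visit's own window but the denominator from the 12-month window

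*Protocol*

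**What the plan says.** The late imaging endpoints are in Protocol C.2.2.4: site-reported endoleak, loss of patency, migration and expansion at 24, 36, 48 and 60 months. Site reporting follows from C.5, which says "An imaging core lab will not be used to perform independent imaging assessments regarding device performance beyond 12 months of follow-up", and from F.3, under which "study sites are to report the results of the imaging performed as standard of care and in line with local and site requirements".

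SAP Table 6 gives the by-visit rate as m/n. At 1, 6 and 12 months both m (subjects with an event) and n (subjects with a readable image) come from the same visit window. The text after the table extends this to 24–60 months and says that the calculation is similar. It then takes m from the window of the specific time point and n from the 12-month window.

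SAP Table 3 sets the windows at days 305–548 (12 months), 549–913 (24), 914–1278 (36), 1279–1643 (48) and 1644–2009 (60). Cumulative image-based rates through 24–60 months are handled separately in SAP 7.9, by interval-censored survival analysis.

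Follow-up beyond 12 months depends on re-consent. C.5 says: "Enrolled subjects who decline to continue to participate in follow-up beyond 12-months shall exit the study upon the completion of their 12-month visit".

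**The concern.** A by-visit rate should be the share of subjects assessed at a visit who show the finding. Under the stated rule, m and n come from different periods and partly different people. A subject with a 12-month image who then declines re-consent, dies, is lost or misses the later scan stays in n at every later visit and cannot contribute an event. A subject without a 12-month image who is scanned at 24 months and has an endoleak is in m but not in n. The result is not a proper proportion.

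Protocol C.1 says that the 60-month follow-up is to provide longer-term evidence on device performance and may support approvals worldwide. If fewer subjects are imaged late than at 12 months, which is the usual pattern, the error lowers the reported late event rates and so favours the device.

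**Working it through.** The plan states no expected late imaging rate, so there is no figure to reproduce. The check compares the stated rule with Table 6 and then works out its effect.

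**1. Do the windows overlap?** No. The 12-month window ends on day 548 and the 24-month window starts on day 549; the later windows follow on. No scan that counts for n can be a scan that counts for m.

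**2. Size of the effect.** Let n_v be the number of subjects with a readable image in the late visit's window, n_12 the number in the 12-month window, and m the number with an event in the late window.

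- Own-window rate (the Table 6 pattern): m/n_v
- Rate as written: m/n_12
- Ratio of the second to the first: n_v/n_12

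The rate is too low when n_v < n_12 and too high when n_v > n_12.

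**3. Illustration.** All counts here are assumptions. Take n_12 = 80 and a true rate of 10% among subjects imaged at the late visit.

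| n_v | m | Own-window rate | Rate as written |
|---|---|---|---|
| 80 | 8 | 8/80 = 10% | 8/80 = 10.0% |
| 60 | 6 | 6/60 = 10% | 6/80 = 7.5% |
| 50 | 5 | 5/50 = 10% | 5/80 = 6.25% |
| 40 | 4 | 4/40 = 10% | 4/80 = 5.0% |

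Because n_12 is fixed while n_v can fall from visit to visit, the error can also create a trend. If the four rows were four successive visits, a constant 10% would be reported as a fall to 5%.

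**4. A smaller cohort.** SAP Table 2 expects at least 63 subjects evaluable at 1 year. That is the number for the device-effect endpoint, not an imaging count, so n_12 = 63 is again only an assumption. Each subject not imaged later lowers the factor by 1/63 = 0.016. Late counts of 57, 50 and 38 give 57/63 = 0.90, 50/63 = 0.79 and 38/63 = 0.60.

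**5. What is not affected.** The 30-day and 1-year tests use the device-effect rate of SAP Table 5. The cumulative late rates use interval-censored methods. None of these uses this n.

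**The case against.** The strongest reply is that this is a drafting slip with an obvious intent. The sentence presents itself as an extension of Table 6, Table 6 matches the windows, and a careful programmer would do the same. The endpoints are descriptive, and the cumulative rates do not use this n. All of that stands, and it is why the point is minor. It does not remove the point: SAP section 3 describes the document as the guideline for the study biostatistician and programmers, and the formula is explicit.

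A reader might infer something stronger from F.3: that contrast imaging is no longer required after 12 months, so that late endoleak rates rest on scans that cannot show an endoleak. The wording invites this, because F.3 also uses standard of care for interim scans ("imaging performed as standard of care beyond the protocol required time points"). The documents do not support it:

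- F.2.4 says "At all required follow-up visits subjects will undergo the following assessments and procedures" and lists contrast chest CT/MRI; its visits include 24–60 months.
- Table F-2, inside F.3, ticks contrast CT/MRI at those visits. Its footnote e allows contrast MRI as the fallback, "with Transesophageal echocardiography (TEE) being an additional option in the event of suboptimal MR imaging", and does not list non-contrast CT or MRI.
- The synopsis says "the assessments as performed during the 12-month visit are to be repeated at 24, 36, 48 and 60 month visits".
- The F.3 sentence directly follows the statement that late images will not go to the core lab. Read with C.5, it changes who reads the scan, not how the scan is done.

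One gap remains. Endoleak is "Defined by the presence of contrast-enhanced blood outside the lumen of the endoluminal graft but within the aneurysm sac", and SAP Table 4 rates CT and MRI without contrast as unable to show it. But SAP 7.2 applies that table only when different image types in one window disagree, and SAP 7.9 does not tie readability to the finding. A lone non-contrast scan entered as negative is therefore not explicitly excluded. Harm would need an off-schedule scan, no contrast scan in the same window, a site entry of no endoleak, and no query. The documents give no basis for sizing that, and they do not show whether the case report form offers a not-assessable option. It merits a clarification, not a finding of error.

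**Conclusion.** The late by-visit denominator in SAP 7.9 is wrong as written. Taken literally, it multiplies the 24-, 36-, 48- and 60-month by-visit rates of endoleak, patency loss, migration and expansion by about n_v/n_12. The bias is downward whenever fewer subjects are imaged at the late visit than at 12 months. The factor follows from the text; its value cannot be estimated, because the documents give no late imaging counts. The values of 0.90 to 0.50 shown for reduced late imaging rest on assumed counts.

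Severity is minor: the rates are descriptive, the intended rule is fairly clear, and no hypothesis test or cumulative estimate is touched. For patency, C.2.2.4 frames the endpoint as up to each time point, so its by-visit rate matters less. The wider inference that the protocol drops contrast imaging after 12 months is not supported.

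**What to change.** In SAP 7.9, define n at 24, 36, 48 and 60 months as the number of subjects with a readable image within the analysis window of that same time point. This is a change of one phrase. It needs no new data, and it brings the late rates into line with Table 6. Reporting n_v beside n_12 at each visit would also show how many subjects were no longer imaged.

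Two optional clarifications:

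- Add a sentence to F.3 that the contrast CT/MRI schedule of F.2.4 and Table F-2 still applies after 12 months and that only the reader changes.
- Tabulate scans rated 4 for endoleak in SAP Table 4 as not assessable. Show this count beside the main rate instead of removing those scans from it: dropping such negatives while keeping every detected event would push the rate upward.
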